Eplerenone is a relatively safe medication, but it can lead to raised serum potassium levels (i.e., hyperkalemia), which can be potentially life-threatening. In a large clinical trial of patients with CHF, the incidence of serious hyperkalemia, defined as a serum potassium concentration ≥ 6 mEq/L, was 5.5% in the eplerenone group and 3.9% in the placebo group. Patients with a lower creatinine clearance at baseline had a higher incidence of serious hyperkalemia.[37]

Eplerenone comes in two doses, 25 mg and 50 mg. The standard dose for treatment of hypertension is 50 mg daily. For patients with an inadequate blood pressure response to 50 mg, the dosage is increased to 50 mg twice daily. For treatment of CHF, patients are started on 25 mg, and escalated to 50 mg within four weeks. Dose adjustment in CHF patients takes place based on serum potassium levels as follows: < 5.0 mEq/L – Increase to 50 mg once daily; 5.0 – 5.4 mEq/L – Maintain dose; 5.5 – 5.9 mEq/L – Decrease to 25 mg every other day; ≥ 6.0 mEq/L – Withhold and restart at 25 mg every other day when potassium levels fall to < 5.5 mEq/L.[38]

The other notable side effects with aldosterone-receptor antagonist medications are related to cross-reactivity with sex hormone receptors. Eplerenone has a much lower incidence of anti-sex hormone effects than spironolactone. With eplerenone, sex hormone-related events, such as breast enlargement in men, breast pain, or menstrual abnormalities, have been reported in up to 2.5% of patients, although some studies reported no such events.[39-41]

Because of the elevations in serum potassium concentrations and consequent increased risk for hyperkalemia with eplerenone, use of this drug is contraindicated in patients at increased risk for hyperkalemia, including those with a serum potassium concentration > 5.5 mEq/L, type 2 diabetes and microalbuminuria, a serum creatinine concentration > 2 mg/dL in men and > 1.8 mg/dL in women, or a creatinine clearance < 50 mL/min, and during concomitant administration of potassium supplements, potassium-sparing diuretics, and/or potent CYP3A4 inhibitors.[38] It is recommended to check serum potassium and creatinine before initiating eplerenone therapy, followed by serum potassium within the first week and at one month after the start of treatment.[38]

Part II

Experimental Protocol:

Study Design

[figure not shown]
- Prospective, consecutive, non-randomized, non-blinded, non-comparative interventional pilot study

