- Eligible patients will be those who present with CSCR, both acute and chronic types
- 20 patients will be enrolled; participation is voluntary and all interested patients must provide written informed consent to take part in the study

- Chronic CSCR will be defined as persistent subretinal fluid on OCT ≥ 3 months after initial presentation to the eye clinic, and $< 50\%$ reduction in fluid thickness on OCT after 3 months.
- Only one eye of a participant will be included in the study, although both eyes will be evaluated. In patients with bilateral CSCR, the worse eye will be the study eye.
- Patients will be evaluated and treated at the New England Eye Center (NEEC)
- All participants will receive a standard ophthalmic examination as well as color fundus photographs, fluorescein angiography, and macular OCT (see below for specific imaging protocol).
- Treatment will be the standard dose of eplerenone, 50 mg pills taken one pill daily over four weeks
- Subjects participation will include 4 visits to the NEEC:
 - o Treatment initiation
 - o 1 week after initiation
 - o 2 weeks after initiation
 - o 4 weeks after initiation
- Prior to initiating treatment, all subjects will have laboratory testing to confirm healthy ranges of the following lab tests will include: serum potassium, creatinine, electrolytes, liver function tests, uric acid, and fasting cholesterol.
- Serum potassium and creatinine levels will be re-tested at the 1 week visit.
- All lab tests will be repeated at the 4 week visit
- Blood pressure will be measured at each visit
- A database of enrolled participants will be maintained on a password protected desktop computer at the New England Eye Center.
- When the study is complete, all data will be de-identified and coded.

Study Assessments/Schematic

Study Protocol

-4 to 5 weeks total
 -20 patients with CSCR (Acute or Chronic)

Initial Diagnosis and Enrollment

1. In order to diagnose CSCR, patients typically undergo a routine ophthalmic examination, fundus photographs, fluorescein angiography, and OCT images. Patients may undergo fundus autofluorescence testing or indocyanine green angiography at the discretion of the physician to confirm the diagnosis of CSCR. These tests are done routinely in the eye clinic and are not included as part of the study protocol.

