4. *Screening Period:* Prior to starting eplerenone therapy, there will be a screening period (≤ 1 week) when serum potassium and creatinine will be evaluated. Patients will be excluded if they have a serum potassium concentration ≥ 5.0 mEq/L, a serum creatinine concentration > 2 mg/dL in men and > 1.8 mg/dL in women, or a creatinine clearance < 50 mL/min, or during concomitant administration of potassium supplements, potassium-sparing diuretics, and/or potent CYP3A4 inhibitors (see below under *Exclusion Criteria*). Additional serum tests of electrolytes, liver function tests, uric acid, and a fasting cholesterol panel will be obtained before initiating therapy. Although there are no exclusion criteria based on these additional laboratory tests, values will be compared to those after 1 month of therapy and abnormalities will be included in safety outcome evaluation at the end of the study. 7.5 to 10 ml of blood will be collected at this visit, as well as a urine sample.
5. Eplerenone is contraindicated in patients who have both type 2 diabetes and microalbuminuria. If a patient has type 2 diabetes, a urinalysis will be performed prior to starting treatment. Patients with type 2 diabetes and microalbuminuria will be excluded from the study.

Eplerenone is considered a pregnancy class B medication, which means that animal reproduction studies have failed to demonstrate a risk to the fetus and there are no adequate and well-controlled studies in pregnant women, or that animal studies have shown an adverse effect, but that adequate and well-controlled studies in pregnant women have failed to demonstrate a risk to the fetus in any trimester. Women of child-bearing potential will be tested for pregnancy at during the initial screening testing, with a urine pregnancy test.

Study Visits

1. After the screening period, patients will come to the NEEC for the first official study visit, the "Treatment Initiation Visit", which includes specific vision screening, blood pressure measurement, and OCT imaging as per study protocol. Patients will be given a bottle containing 28 tablets of eplerenone 50mg, and will start eplerenone the same day. Medication will be provided by the Tufts Research

Pharmacy. Patients will then return to the clinic at 1 week, 2 weeks, and 4 weeks after baseline.

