5. *Fluorescein Angiography*: Fluorescein angiography will be acquired at diagnosis and at 4 weeks after treatment initiation. Angiography will be explained to patients by either the physician or the ophthalmic nurse administering the intravenous dye. Patients routinely give verbal consent stating they understand the procedure and potential risks of fluorescein angiography. The procedure involved a special water-soluble dye (fluorescein) that is injected intravenously. As the dye passes through the blood vessels of the choroid and retina, the photographer takes a series of photographs in rapid succession, over a period of 5-10 minutes. The possible side effects of fluorescein angiography are discussed below.

Laboratory Testing: After initial screening, serum potassium and creatinine will be evaluated at 1 and 4 weeks after baseline. *See below for dosing adjustment instructions based on potassium levels.* Additional serum tests of electrolytes, liver function tests, uric acid, and a fasting cholesterol panel will be obtained before treatment and 4 weeks after baseline

Baseline and 4-week visits: Serum potassium, sodium, BUN, creatinine, glucose, chloride, total CO₂, calcium, AST, ALT, GGT, alkaline phosphatase, total and direct bilirubin, uric acid, albumin, total protein, fasting total cholesterol, fasting LDL, fasting LDL, fasting triglycerides. The initial and final blood draws will be roughly 7.5 to 10 ml of blood, or 2 teaspoons.

6. **1-week visit:** Serum potassium and serum creatinine. The 1-week blood draws will be roughly 4 ml of blood, or 1 teaspoon.

7. **Blood pressure:** Systolic and diastolic blood pressure will be recorded at all visits. Blood pressure will be measured in the seated position. When blood pressure is scheduled at the same time point as a blood sample draw, the blood pressure will be measured first.

8. The subject's participation in the research may be terminated by the principal investigator or co-investigator if there is any type of medical emergency or urgency that needs to be attended to first. If a subject decides to withdraw from the research, the patient will be offered routine ophthalmologic care at NEEC. If the patient prefers, he or she can be referred to an outside ophthalmologist for continued eye care. The subject's data and collected blood and urine samples will be discarded, although the reason for screen failure will be noted after the patient demographic data is de-identified.

Eligibility

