- Change in best-corrected visual acuity before and after 4 weeks of treatment
- Change in dye leakage characteristics on fluorescein angiography before and after 4 weeks of treatment
- Change in the same OCT characteristics listed above, in the fellow eye
- Proportion of acute vs. chronic CSCR patients
- Safety and tolerability characteristics in this patient population via clinical laboratory data, blood pressure, and adverse events

Data Safety and Monitoring Plan

See below for details regarding monitoring of adverse events (AEs) and serious adverse events (SAEs). Data will be monitored with the patients' safety in mind. All adverse effects will be recorded by the Principal Investigator and Co-Investigators and will be reported to the IRB at the conclusion of the study. Should an SAE occur, it will be reported immediately to the Tufts MC / TUHS IRB by the Principal Investigator within 24 hours. The Principal Investigator and Co-Investigators will be responsible for collecting the patient data information. The information will then be de-identified and coded. The key to the code will only be accessed by the investigators.

Dose adjustment and/or stopping criteria

Serum potassium criteria

If serum potassium is ≥ 5.0 mEq/L and < 5.5 mEq/L at 1 week after initiation, dosing will be decreased to 25 mg every day and serum potassium will be rechecked at 1 week. If serum potassium is still ≥ 5.0 mEq/L and < 5.5 mEq/L after 1 additional week, dosing will be decreased to 25 mg every other day and serum potassium will be rechecked at 1 week. If serum potassium is still ≥ 5.0 mEq/L and < 5.5 mEq/L after 1 additional week, dosing will be withheld. If serum potassium is ≥ 5.5 mEq/L at 1 week, eplerenone will be withheld.

See below for definition of adverse events and serious adverse events.

Statistical Analysis

The primary outcome will be described by the proportion of patients without subretinal fluid on OCT at the end of the study period (see below for sample size and precision estimates). The 95% confidence interval (CI) for this proportion will also be estimated. Descriptive statistics are considered appropriate for this pilot study since there is currently no standard treatment for CSCR, and the data from this study may be used to design future, rigorous trials of eplerenone.

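### A week-1 potassium of 5.5 mEq/L or more stops eplerenone, but no repeat potassium is required until week 4, and the wording leaves unclear whether the same stop applies at later rechecks

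*Combined protocol and SAP*

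**What the plan says.** The rules are in the combined protocol and SAP under Dose adjustment and/or stopping criteria, Serum potassium criteria.

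- **Potassium 5.0 to below 5.5 mEq/L.** At week 1 the dose drops to 25 mg daily, with a recheck a week later. A second value in the band drops it to 25 mg on alternate days, with another recheck. After a third: "If serum potassium is still ≥ 5.0 mEq/L and < 5.5 mEq/L after 1 additional week, dosing will be withheld".
- **Potassium 5.5 mEq/L or more.** The whole instruction is "If serum potassium is ≥ 5.5 mEq/L at 1 week, eplerenone will be withheld".

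The routine laboratory schedule is under Study Visits, Laboratory Testing: "After initial screening, serum potassium and creatinine will be evaluated at 1 and 4 weeks after baseline". The Study Design list agrees. It has potassium and creatinine at week 1, and then "All lab tests will be repeated at the 4 week visit". Clinic attendance is more frequent than that: "Patients will then return to the clinic at 1 week, 2 weeks, and 4 weeks after baseline". No laboratory test is listed for the week-2 visit. Part IV, under potential risks, tells participants to expect three blood draws in all.

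Under Definition of Serious Adverse Events, a potassium of 6.0 mEq/L or more at any time on treatment is an SAE.

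**The concern.** The background section describes hyperkalemia as potentially life-threatening, and safety is both an aim and an outcome of this off-label study. Stopping the drug is the main protection after a high value, and the plan does that. What it does not require is any confirmation that the potassium has come down. The patients with the highest week-1 values leave the potassium ladder with no test ordered, and they can attend the week-2 visit without having blood drawn.

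A second difficulty concerns patients already on a reduced dose. Both later ladder steps act only on values that are still between 5.0 and 5.5, while the stop at 5.5 or more is tied to 1 week. If that means one week after initiation, a patient whose potassium rises to 5.5 or more on the reduced dose has no stated instruction to stop.

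**Working it through.** The plan gives no figure of its own on this point. Its confidence-interval table is not involved. The check is calendar arithmetic plus a reading of which values each sentence covers.

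**Inputs.** Weeks 1, 2, 3 and 4 are days 7, 14, 21 and 28. Required post-baseline potassium tests are on days 7 and 28 (Study Design; Laboratory Testing). Clinic visits after initiation are on days 7, 14 and 28 (Study Visits). Rechecks on days 14 and 21 exist only for patients in the 5.0 to below 5.5 ladder.

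**Week-1 value of 5.5 or more, drug stopped.**
- Time to next required potassium: 28 − 7 = 21 days.
- With a draw at the existing week-2 visit: 14 − 7 = 7 days.

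**Does other text order a retest?**

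| Text | What it provides | Repeat potassium required? |
|---|---|---|
| AE definitions and recording | Investigator review of clinically significant laboratory values | No |
| SAE rule at 6.0 or more | Report to the IRB within 24 hours | No |
| Study Visits, item 8 | Participation may be ended "if there is any type of medical emergency or urgency that needs to be attended to first" | No |
| Detection and reporting of harmful effects | Emergency care if a problem occurs | No |

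**Later recheck of 5.5 or more, literal reading.** The ladder's next recheck is triggered only by a value in the 5.0 to below 5.5 band, so the next required test is week 4.
- From the week-2 recheck, on 25 mg daily: 28 − 14 = 14 days.
- From the week-3 recheck, on 25 mg on alternate days: 28 − 21 = 7 days.

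**How firm is the literal reading?** The opening sentence of the rule dates the first test from initiation, and recheck results are described as coming after one additional week. Both favour reading the stop at 5.5 as a week-1 rule. Against that, the rechecks themselves are said to happen at 1 week, and the sentence on 5.5 or more comes after the whole ladder and drops the reference to initiation. The text therefore supports two readings, with the week-1 reading the more literal.

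**Blood volume.** Planned: 2 × (7.5 to 10 ml) + 4 ml = 19 to 24 ml. One extra 4 ml draw adds 4/24 = 17% to 4/19 = 21%.

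**The case against.** The strongest reply is that the plan is already cautious. It stops drug at 5.5, whereas the heart-failure dosing quoted in the background only reduces the dose at 5.5 to 5.9 and stops at 6.0. Screening excludes potassium of 5.0 or more and creatinine clearance below 50 mL/min. Tests at weeks 1 and 4 match the monitoring the protocol cites from the label. A high value would be reviewed by the investigator, a value of 6.0 or more would be reported, and a clinician may retest at any time. All of this stands and reduces the risk. However, weeks 1 and 4 are routine monitoring rather than follow-up of an abnormal result, and none of these safeguards requires the repeat.

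A reader might also infer stronger points that the documents do not support.

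- **That the plan certainly omits a stop at later rechecks.** The wording can be read to cover them, and the ladder's direction points the same way, since a third value in the lower band already stops drug. This is an ambiguity.
- **That milder values get better follow-up than severe ones.** The 1-week rechecks in the lower band are for patients still taking drug, so the comparison is not like for like.
- **That a chance of the event among 20 patients can be given.** The nearest figure is the heart-failure trial's rate of serious hyperkalemia, which "was 5.5% in the eplerenone group and 3.9% in the placebo group". That is a different population and a cut-off of 6.0, and it is not tied to week 1.
- **That the undefined term for stopping is itself a defect.** The heart-failure rule reads "Withhold and restart at 25 mg every other day when potassium levels fall to < 5.5 mEq/L", but it is background, and the trial's own rule sits under stopping criteria in a four-week course with no restart provided. Saying that the stop is permanent would be an optional clarification.

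**Conclusion.** The point holds. After a week-1 potassium of 5.5 mEq/L or more, including SAE-level values, the plan requires no repeat until week 4. The gap is 21 days, assuming the patient stays in follow-up after stopping drug, which the plan does not settle. A draw at the planned week-2 visit would cut it to 7 days. This part rests on the plain text.

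The second part is less certain. On the more literal reading, a value of 5.5 or more at the week-2 or week-3 recheck has no stated stop, leaving 14 or 7 days on reduced dose before the next required test. On the broader reading there is no missing stop, only unclear wording. A stopping rule should not depend on which reading site staff choose.

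The documents do not say how potassium behaves once eplerenone is stopped, and they give no rate of such values in this population, so neither the clinical harm nor its frequency can be sized. The primary estimate is not affected. The plan should be changed because, followed literally, it leaves the patients with the highest values unchecked for three weeks, and the remedy is cheap.

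**What to change.** Amend the serum potassium criteria to say:

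1. Any on-study potassium of 5.5 mEq/L or more, at week 1 or at any recheck, stops study drug.
2. Potassium is then repeated within 7 days, and sooner at 6.0 mEq/L or more. For a week-1 value the repeat is drawn at the existing week-2 visit. For a week-3 value the scheduled week-4 test serves.
3. Further repeats are at the investigator's discretion until the value reaches a limit set by the medical lead.

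In Part IV, note that the three draws are the routine schedule and that a raised potassium may need more. The existing ladder already implies this.

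**Cost.** A short wording amendment and, in the few patients affected, usually one extra draw of about 4 ml. A week-2 recheck of 5.5 or more needs an extra visit, as does an earlier repeat at 6.0 or more. Further discretionary repeats would add to this.

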Changes in continuous secondary outcome measures will be described using mean, median, min/max, and standard deviations, and categorical secondary outcome measures will be described using frequencies and proportions.

Sample Size and Precision Calculations

The natural history of acute CSCR is to improve on its own. Studies have shown, however, that fluid resolution typically takes at least 6 weeks, and often takes as long as 3 months or longer. In a randomized study by Chan et al examining effects of half-dose photodynamic therapy in patients with acute CSCR, 20% of patients had complete resolution of fluid on OCT after 4 weeks, compared to 80% of patients treated with PDT.[12] Similar rates of complete fluid resolution have been reported after treatment with PDT, as well as in a small sample of patients with chronic CSCR treated with eplerenone.[1, 22-26] Based on these assumptions, a calculation was performed to determine the width of confidence intervals for the proportion of patients successfully

treated with eplerenone. If the treatment is effective for 70% of patients, a sample size of 10 patients will give a 95% confidence interval width of 0.586 that includes a lower bound of 0.348 (see range of widths with sample sizes of 10 and 15 below). The Research Design Center of the Clinical and Translational Sciences Institute at Tufts Medical Center assisted with these calculations.

Numeric Results for Two-Sided Confidence Intervals for One Proportion Confidence Interval Formula: Exact

Confidence Level	Sample Size (N)	Target Width	Actual Width	Proportion (P)	Lower Limit	Upper Limit	Width if P = 0.5
0.950	10		0.586	0.700	0.348	0.933	0.626
0.950	10		0.531	0.800	0.444	0.975	0.626
0.950	10		0.442	0.900	0.555	0.997	0.626
0.950	15		0.487	0.700	0.416	0.903	0.522
0.950	15		0.438	0.800	0.519	0.957	0.522
0.950	15		0.356	0.900	0.637	0.993	0.522

References

Flleiss, J. L., Levin, B., Paik, M.C. 2003. Statistical Methods for Rates and Proportions. Third Edition. John Wiley & Sons. New York.
 Newcombe, R. G. 1998. 'Two-Sided Confidence Intervals for the Single Proportion: Comparison of Seven Methods.' *Statistics in Medicine*, 17, pp. 857-872.

Safety Analysis

Safety data will be presented in tabular format and will be summarized descriptively.

PART III

1. How will participants be recruited?
 Participants will be recruited from the practices of the primary investigator and co-investigators.
2. Number of participants needed?

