 The maximum number of participants over the entire study is expected to be 20.
3. Will participants receive any payment or other compensation for participation?
 No. There are no costs to subjects participating in this research study and he or she will not be billed for the visit. Eplerenone will be provided by the New England Eye Center.
4. Will participants be studied outside NEEC premises?
 No.

5. Will the facilities of the Clinical Research Center be used?
No.
6. Will drugs be used?
Yes. Eplerenone 50mg, an oral medication FDA-approved for use in systemic hypertension and congestive heart failure, will be used off-label for treatment of all patients in this study. Patients will be provided the medication by the investigational team. Funding is being provided by the Research Fund of the Ophthalmology Department at Tufts Medical Center.
7. Will radiation or radioactive materials be employed?
No.
8. Will special diets be used?
No.
9. Will participants experience physical pain or stress?
While some patients experience distorted vision as a result of CSCR, no additional physical distress to patients is expected as a result of this study.
10. Will a questionnaire be used?
No.
11. Are personal interviews involved?
No.
12. Will participants experience psychological stress?
No.
13. Does this study involve planned deception of participants?
No.
14. Can information acquired through this investigation adversely affect a participant's relationships with other individuals?
No.
15. Please explain how subjects' anonymity will be protected, and/or confidentiality of data will be preserved.
The data obtained from the study will be retained by [name] and will be stored at NEEC for a minimum of 8 years per institutional policy. Members of the research study team including the principle and co-investigators will analyze the data. If results of this study are reported in medical journals or at meetings, subjects will not be identified by name, by

recognizable photograph, or by any other means. The subjects' medical records will be maintained according to the NEEC requirements.

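### Does giving precision for 10 and 15 patients, when 20 are to be enrolled, leave the sample size unsupported?

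*Combined protocol and SAP*

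**What the plan says.** The Study Design list states that "20 patients will be enrolled". Part III, item 2 words the same number as a ceiling: "The maximum number of participants over the entire study is expected to be 20". Acute and chronic disease are recruited together ("Eligible patients will be those who present with CSCR, both acute and chronic types"), with no target for either type.

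Statistical Analysis defines a single primary summary: "The primary outcome will be described by the proportion of patients without subretinal fluid on OCT at the end of the study period". It adds: "The 95% confidence interval (CI) for this proportion will also be estimated". The reader is sent to the next section for the precision estimates.

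That section, Sample Size and Precision Calculations, assumes 70% success and says that "a sample size of 10 patients will give a 95% confidence interval width of 0.586", with a lower bound of 0.348. It then points to a table: "see range of widths with sample sizes of 10 and 15 below". The table gives exact two-sided 95% intervals at success proportions of 0.70, 0.80 and 0.90 for each of the two sizes. Twenty does not appear there as a sample size, and nothing says what 10 and 15 stand for.

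Study Visits, item 8 bears on how many patients will be analysed. For a subject who withdraws: "The subject's data and collected blood and urine samples will be discarded". No withdrawal rate is given.

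**The concern.** The plan contains no power calculation, hypothesis test or success criterion. Confidence interval width is the only numerical argument for the size of the study, and Statistical Analysis ties it to the primary outcome. If that argument is made for 10 and 15 patients while 20 are enrolled, the printed precision is not that of the planned design, and the choice of 20 is not explained.

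None of the obvious explanations is written down. Two equal groups by disease type would account for 10 but not for 15. An allowance for losses would have to be 25% to reach 15, or 50% to reach 10. An ethics committee might ask why 20 people should take an off-label drug when the stated case stops at 15. Someone designing a later trial from this pilot might take 0.586 as the precision to expect.

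**Working it through.** **Inputs.** From Sample Size and Precision Calculations: two-sided 95% confidence, exact formula, success proportions P of 0.70, 0.80 and 0.90, and N of 10 and 15. From Study Design and Part III, item 2: 20 patients.

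**Formula.** The exact (Clopper-Pearson) limits with x = N × P successes are:

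- lower = 2.5% quantile of Beta(x, N − x + 1)
- upper = 97.5% quantile of Beta(x + 1, N − x)

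**Reproducing the plan's table.** All six rows agree to within 0.001.

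| N | P | x | Recomputed | Width | Plan's limits | Plan's width |
|---|---|---|---|---|---|---|
| 10 | 0.70 | 7 | 0.3475–0.9333 | 0.5857 | 0.348–0.933 | 0.586 |
| 10 | 0.80 | 8 | 0.4439–0.9748 | 0.5309 | 0.444–0.975 | 0.531 |
| 10 | 0.90 | 9 | 0.5550–0.9975 | 0.4425 | 0.555–0.997 | 0.442 |
| 15 | 0.70 | 10.5 | 0.4158–0.9026 | 0.4868 | 0.416–0.903 | 0.487 |
| 15 | 0.80 | 12 | 0.5191–0.9567 | 0.4376 | 0.519–0.957 | 0.438 |
| 15 | 0.90 | 13.5 | 0.6366–0.9927 | 0.3561 | 0.637–0.993 | 0.356 |

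The widths at P = 0.5 also agree: 0.626 for N = 10 and 0.522 for N = 15. There is no arithmetic error.

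**The same formula at N = 20, everyone analysed.**

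| P | x | Interval | Width |
|---|---|---|---|
| 0.70 | 14 | 0.457–0.881 | 0.424 |
| 0.80 | 16 | 0.563–0.943 | 0.379 |
| 0.90 | 18 | 0.683–0.988 | 0.305 |
| 0.50 | 10 | 0.272–0.728 | 0.456 |

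**Size and direction at P = 0.70.** The plan's N = 10 width exceeds the N = 20 width by 0.586 − 0.424 = 0.162, which is 0.162 / 0.424 = 38%. The N = 15 width exceeds it by 0.487 − 0.424 = 0.063, or 0.063 / 0.424 = 15%. The lower limit rises from 0.348 (N = 10) or 0.416 (N = 15) to 0.457. The printed figures therefore err on the cautious side.

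**If fewer than 20 are analysed.** Losses needed to reach the printed rows are (20 − 15)/20 = 25% and (20 − 10)/20 = 50%. Between those sizes the printed rows bracket the precision; above 15 they understate it. As an illustration only, since the documents give no loss rate, suppose 16 or 18 are analysed. Seventy percent of these is 11.2 and 12.6 patients, so the results that could occur on either side are:

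- 11/16: 0.413–0.890, width 0.476
- 12/16: 0.476–0.927, width 0.451
- 12/18: 0.410–0.867, width 0.457
- 13/18: 0.465–0.903, width 0.438

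All four are narrower than the plan's 0.487 for N = 15 at 0.70.

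**Where the figures are used.** Statistical Analysis compares the proportion with no reference value and sets no target for the lower limit. Neither the potassium-based dosing rules nor the safety monitoring refers to interval width. The tabulated widths are read once, at planning, and enter no later decision.

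**The case for a change.** The strongest case for a change is that a sample-size section should state the precision of the planned sample. This one does not, and every explanation of 10 and 15 is a guess. Adding a row for 20 and a label on the others would cost almost nothing, and the pilot is meant to inform later trials. All of that is true, and it stands as an observation about completeness.

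It does not amount to a fault in the plan. The text never presents 0.586 as the precision of 20 patients; it labels the figure as that of 10. Twenty is worded as a maximum. Consent is taken at the diagnosis visit and the laboratory exclusions follow, so it is not settled whether 20 counts consented or treated patients. Screen failures, withdrawals with discarded data, or slow recruitment could each bring the analysed number down towards 15 or below. The existing rows are then the useful ones, and deleting them would lose information. A later designer will also work from the observed interval and its denominator, not from a planning table.

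**Conclusion.** No change follows. The mismatch is real: 20 is the planned maximum, and precision is shown only for 10 and 15 without explanation. Every printed figure is nevertheless right for its own sample size. At 70% success the full 20 would give a width of 0.424, against printed widths of 0.586 and 0.487, so the design is more precise than the section suggests and is not too small by its own figures. An analyst following the plan will report the observed proportion with its 95% interval at the number actually analysed, and anyone who wants the planning figure for 20 can obtain it from the exact formula the table names.

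This rests on two conditions. The exact method named in the table must also be the one used for the reported interval. And at least 10 patients must be analysed, because below that the precision would be worse than anything printed at the same proportion; from a full 20 this would take a loss of more than half, and the documents give no rate by which to judge it.
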